6.11 Visit Windows

Assessments during the treatment period (Days 4 to 15) that are not obtained on the scheduled day will be assigned to the nearest scheduled day. For example, a PCSS assessment performed on Day 12 will be assigned to Day 11 for the purposes of 'by visit' summaries, unless the assessment was inadvertently obtained in addition to the Day 11 assessment.

Assessments after the end of treatment that are not obtained within the scheduled window will be assigned to the nearest scheduled day (Day 21 or 44). For example, if the QOLIBRI assessment was not obtained until Day 25, it would still be assigned to Day 21 for the purposes of 'by visit' summaries.

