This statistical analysis plan (SAP) provides details on the study design, outcome measures and data analyses planned for the exploratory study of ghrelin (OXE-103) in subacute and acute concussion management that is being conducted at the University of Kansas Health System Center for Concussion Management (CCM). The outcome measures and data analyses specified in this SAP supersede any specified in the study protocol, if differences exist.

Any deviations from this plan will be documented in the clinical study report, and will include timing of changes in relation to unblinding of the study.

Pharmacokinetic, anti-ghrelin antibody and/or biomarker samples may be collected for future use and any data analysis will be the subject of a separate SAP.

2. Study Design

This subacute and acute concussion management study will be conducted as a randomized, single center, double-blind, placebo-controlled, parallel group design in two distinct parts. In Part A, subjects will be recruited from the University of Kansas Health System CCM clinics which include Neurology, Sports Medicine, and Neurosurgery/Physical Medicine and Rehabilitation. Subjects who provide written informed consent and satisfy enrollment criteria at the end of a 7-day screening period will be randomized in a 1:1 manner to either the OXE-103 or placebo treatment groups. In Part B, subjects will be recruited from the emergency department and enrolled within 24 hours of injury. Treatments will be self-administered subcutaneously twice daily during a 14-day treatment period; the OXE-103 group will receive 40 µg/kg with each dose.

For Part A, clinic visits will be conducted at the start of Screening (Day -7), Randomization (Day 1), Day 8, End of Treatment (Day 15), 1 week after the end of treatment (Day 21) and End of Study (Day 44).

Phone contacts will be done during Screening (Day -3) and during treatment (Days 4 and 11). Part B subjects will follow the same schedule except that there will be no screening visit or phone contact.

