5.1 Primary Efficacy Outcome Measures

- PCSS severity responder as defined by $\geq 20\%$ improvement over baseline at Day 15 in the severity score
- PCSS symptom responder as defined by $\geq 20\%$ improvement over baseline at Day 15 in the number of symptoms
- PCSS 4MBS responder as defined by $\geq 20\%$ improvement over baseline at Day 15 in the 4MBS severity score
- Change from baseline in PCSS severity score at each post-baseline assessment (Days 4, 8, 11, 15, 21 and 44)
- Change from baseline in PCSS number of symptoms at each post-baseline assessment (Days 4, 8, 11, 15, 21 and 44)
- Change from baseline in PCSS 4MBS severity score at each post-baseline assessment (Days 4, 8, 11, 15, 21 and 44)

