6.1 General Methods

This pilot study will describe changes observed in the two treatment groups, placebo versus OXE-103, separately for each part. Since the study is exploratory, analyses will focus on descriptive comparative statistics and not on a pre-specified statistically significant primary endpoint. Data will be used to enable power calculations and the definition of suitable clinical endpoints for further clinical development. Data from baseline and on Study Days 4, 8, 11, 15, 21, and 44 will be analyzed. Note that day definitions in this study will follow the Clinical Data Interchange Standards Consortium in that there is no Day 0;

assessments performed prior to randomization will be done on Days -7 and -3 (Part A only) and randomization is considered Day 1.

For all evaluations of changes from baseline, baseline is defined as the last reported value before the first dose of study drug. In most instances, this will be the value recorded on Day 1.

For the evaluation of safety, a treatment-emergent finding is any result that is newly reported after the first dose of study drug. This may include an existing condition which worsens in severity after the start of treatment.

Continuous variables such as total score or change from baseline will be summarized by the number of observations, mean, standard deviation, median, minimum and maximum value. Graphs of changes from baseline over time will present the means and 95% confidence intervals.

Binary or categorical variables will be summarized by the number of observations in each category along with the percent of observations.

To aid in interpretation of the importance of relationships, correlation coefficients (Pearson and Spearman) will be reported with p-values.

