6.10 Missing Data Handling

For responder analyses, the last available post-baseline value will be used for patients who do not have an assessment on Day 15. No other data will be imputed.

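### SAP 6.11, read by the day performed, assigns an end-of-treatment assessment done on Day 16 or 17 to Day 21, and SAP 6.10 does not say whether the value then used for the Day 15 responder outcomes must be earlier or may be later

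*SAP*

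**What the plan says.** SAP 6.11 has two rules, divided at the end of treatment. The first reads: "Assessments during the treatment period (Days 4 to 15) that are not obtained on the scheduled day will be assigned to the nearest scheduled day". The second covers assessments after the end of treatment. Those "not obtained within the scheduled window will be assigned to the nearest scheduled day (Day 21 or 44"; no other target is offered. Each rule has one worked example: Day 12 is assigned to Day 11, and Day 25 to Day 21. Both examples say that the assignment serves the by-visit summaries.

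SAP section 2 lists the visit as "End of Treatment (Day 15"). The protocol schedules of events allow ±1 day at Day 8, ±1 at Day 21 and ±3 at Day 44. They allow nothing at Days 4, 11 or 15.

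The first responder outcome in SAP 5.1 requires at least 20% "improvement over baseline at Day 15 in the severity score". The symptom-count and 4MBS responders use the same day. For these outcomes SAP 6.10 states that "the last available post-baseline value will be used for patients who do not have an assessment on Day 15", and it rules out imputation of anything else.

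**The concern.** Taken together, the two rules in 6.11 leave a gap just after the primary time point. Early or mid-treatment assessments go to whichever target is closest. One made a day after Day 15 can go only to Day 21 or 44. Day 15 has no tolerance, so even a one-day slip falls outside the first rule.

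Three things follow for such a subject:
- The Day 15 change from baseline is missing for the PCSS measures and for any secondary measure taken at the same late visit.
- Responder status is read from a substituted value although a real end-of-treatment value was collected.
- Two values can compete for Day 21, and the SAP deals with duplicates only in its Day 11 example.

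The subject stays in the efficacy analysis. The per-protocol set in SAP 6.2 asks for a Day 8 PCSS but not a Day 15 one. In Part A, which the current protocol makes open-label against an untreated control, a choice left open in the SAP could be made with the arms known.

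**Working it through.** **Inputs.** The target days come from SAP 6.1: "Data from baseline and on Study Days 4, 8, 11, 15, 21, and 44 will be analyzed". The first rule of 6.11 chooses among {4, 8, 11, 15} for assessments up to Day 15. The second chooses among {21, 44} afterwards. Distance = |day performed − target day|.

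**The SAP's own examples.** Day 12: |12−11| = 1 and |12−15| = 3, so Day 11. Day 25: |25−21| = 4 and |25−44| = 19, so Day 21. Both are reproduced.

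**Days around Day 15.**

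| Day performed | Distance to 15 | Distance to 21 | 6.11 by day performed | Nearest of all six targets |
|---|---|---|---|---|
| 14 | 1 | 7 | 15 | 15 |
| 16 | 1 | 5 | 21 | 15 |
| 17 | 2 | 4 | 21 | 15 |
| 18 | 3 | 3 | 21 | tie, 15 or 21 |
| 19 | 4 | 2 | 21 | 21 |

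The rule departs from true nearest-day assignment on Days 16 and 17. Day 18 is a tie that the rule happens to settle.

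**What the responder analysis then uses.**
- *PCSS on Days 4, 8, 11, 16, 21 and 44.* Day 15 is empty and Day 21 holds two values. If carrying is limited to values before Day 15, the Day 11 value is used. If 6.10 is taken literally, the Day 44 value is used.
- *PCSS on Days 4, 8, 11 and 17, nothing later.* The limited reading uses Day 11. The literal reading uses the Day 17 value itself.

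The same sentence in 6.10 can therefore give a value from before Day 15 or from well after it. In both cases the Day 15 change from baseline is missing.

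**Ties.** Day 6: |6−4| = |8−6| = 2. Day 13: |13−11| = |15−13| = 2. No tie rule is given. Take a subject seen on Days 4, 8 and 13, with no separate Day 11 or Day 15 assessment. With carrying limited to values before Day 15, the responder value is the Day 13 value whether the tie goes to Day 11 or Day 15.

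**Size per subject.** Responder rate = responders / n. With the target of 20 per arm, one changed status moves the rate by 1/20 = 5 points. With 25 per arm (the Part B maximum of 50, split equally), it moves by 1/25 = 4 points. How many subjects are affected cannot be computed from the documents.

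**The case against.** The strongest counter-argument concerns how 6.11 is read. Its first sentence could refer to assessments *scheduled* for Days 4 to 15. A Day 15 assessment done on Day 16 would then be a treatment-period assessment off its day, and it would return to Day 15. The second sentence speaks of scheduled windows, which Days 21 and 44 have and Day 15 lacks, and its Day 25 example looks like a late Day 21 visit. This reading is possible. However, if each assessment already belonged to its scheduled visit, there would be no reason to look for the nearest day, and both examples are phrased by when the assessment took place. Even if the two readings were equally good, two analysts could build different Day 15 data.

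A second argument is that 6.11 governs only by-visit summaries. This does not rescue the responder outcomes. Without 6.11, a Day 16 value is still not an assessment on Day 15, and 6.10 applies.

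A third is that the study is descriptive: "analyses will focus on descriptive comparative statistics and not on a pre-specified statistically significant primary endpoint". That stands, and it limits how much weight the point carries.

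A reader might also infer more than the documents support:
- *The lost value is replaced by an earlier one, so response is understated.* SAP 6.10 does not limit the carried value to days before Day 15, so the direction is open. A figure for the bias would need a late-visit rate and response rates at two time points, and none is given. Similar lateness in both arms would partly cancel in the comparison.
- *The ties lose the primary time point.* Day 13 may be assigned to Day 15, a true Day 15 assessment takes precedence if there is one, and Day 6 does not touch Day 15.
- *The Day 21 summary is distorted.* By analogy with the Day 11 exception, an actual Day 21 assessment could be kept and the extra one set aside. The SAP does not say so, but distortion is not shown.

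**Conclusion.** The point holds as a defect in a stated rule. Read by the day performed, which fits the wording better, 6.11 moves a Day 16 or 17 end-of-treatment assessment away from the closer primary time point. The Day 15 change from baseline is then missing. The three responder outcomes rest on a carried value that may be earlier or later than Day 15, so the direction of bias is not determined.

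The total effect is unknown because the documents give no late-visit rate. Per subject it is 5 points in an arm of 20, and only if the subject's status differs between the two values. This assumes that a visit one or two days late is not itself classed as a major deviation, which would remove the subject from the per-protocol set; the SAP does not list what counts as major. The missing tie rule for Days 6 and 13 is secondary.

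Since this pilot is meant to inform later endpoints and power calculations, the point is worth settling before the data of either part are locked.

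**What to change.** Replace 6.11 with a table of contiguous analysis windows and state that it governs both the by-visit summaries and the responder outcomes. One workable set, with boundaries at the midpoints between targets and ties sent to the later target:

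| Target | Analysis window |
|---|---|
| Day 4 | Days 2-5 |
| Day 8 | Days 6-9 |
| Day 11 | Days 10-12 |
| Day 15 | Days 13-17 |
| Day 21 | Days 18-32 |
| Day 44 | Day 33 onward |

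If a window holds more than one assessment, use the one closest to target and, if equally close, the later one. In 6.10, state that the Day 15 responder value is the value in the Day 15 window. If there is none, any carried value must come from before that window opens.

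In the first worked subject above, Day 15 would then hold the Day 16 value and Day 21 its own value. In the second, Day 15 would hold the Day 17 value.

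The cost is a short SAP table and one added sentence, with no new data. The small downside is that values up to 2 days off target count as Day 15, including a Day 13 value taken before dosing ends on Day 14. The upper limit of the Day 21 window changes nothing, because the present rule already sends Day 32 to Day 21 (11 days away, against 12 to Day 44).

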6.12 Subgroup Analyses

No subgroup analyses are currently planned for this exploratory study.

6.13 Adjustment for Covariates

No statistical modeling is planned for this exploratory study, therefore, there will be no adjustment for covariates.

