Subjects are presented with study drug (OXE-103) treatment. If they decline, they will be offered participation in non-treatment control Arm. If subjects choose treatment and fail screening, they may be offered non-treatment control Arm option.

PART A ARM 1 = OXE-103 treatment

PART A ARM 2 = Non-treatment concurrent control

[figure not shown]

PART B: ACUTE DAY 1

Subjects choosing to participate in study are randomized to receive study drug (OXE-103) or placebo.

PART B ARM 1 = OXE-103

PART B ARM 2 = Placebo

Regulatory:

Oxeia's license through Daiichi Sankyo includes cross-reference to an open IND at the FDA. In November 2017 Oxeia submitted a pre-IND briefing package for a proposed Phase 2 study. The FDA response supported moving into Phase 2. This study will be conducted under an investigator sponsored IND cross referencing the existing open FDA IND.

Manufacturing, Partnerships, Current GMP Drug Supply:

The company maintains access to clinical grade drug supply manufactured by Daiichi Sankyo, Ltd. for subcutaneous injection. Multiple lots have been produced and are available for clinical study use. The drug product is manufactured in compliance with good manufacturing practice. It is supplied in a 5 mL clear, borosilicate glass vial with a butyl-rubber closure (fluoro-resin film laminated), as a sterile lyophilized white powder or cake equivalent to 14 mg of OXE-103 as the active ingredient and sucrose (inactive ingredient). Matching placebo and diluent product is also available.

OXE-103 drug product, placebo, and diluent should be stored refrigerated between 2°C to 8°C (35.6°F to 46.4°F). Reconstituted OXE-103 for SC administration 14 mg (in 5 mL multi-use vials) is stable for up to 14 days at 10°C or for up to 3 days when stored at 25°C/1000 Lux. The reconstituted drug product (and placebo) should be stored refrigerated at 2°C to 8°C (35.6°F to 46.4°F).

Upon request from the study team, Oxeia Biopharmaceuticals will coordinate shipment of all necessary study drug product, placebo, and diluent to the study team. Shipments will include all appropriate certificates of quality, as may be necessary for any FDA-related audits and submissions.

Proposed Clinical Trial

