We propose a pilot study to treat 1) Sub-acute concussion with OXE-103 in Part A and 2) Acute concussion management with OXE-103 within 24 hours of presentation to the Trauma Unit in Part B. For Part A, we will recruit subjects from the University of Kansas Health System Center for Concussion Management (CCM) clinics which include Neurology, Sports Medicine, and Neurosurgery/PM&R. For Part B, we will recruit subjects from the University of Kansas Health System Trauma Unit. In Part A we will compare an open-label treatment arm (OXE-103) to a non-treatment concurrent control arm. Part B will be randomized double blind 1:1 to treatment with OXE-103 and placebo. We will compare these using self-report symptom scoring, quality of life questionnaires, computerized cognitive testing assessing executive function, memory and processing speed, and accelerometer-based balance scoring. The exploratory nature of this study is not powered to yield statistically significant outcomes, but will allow detection of trends within subjects and between groups, will support comparison with standard tests of neurocognitive functions, and will provide sample size estimates for future studies of people with persistent concussion related symptoms.

This study is highly relevant clinically and uniquely suited to being conducted at the CCM. It will be the first to test ghrelin as therapy for sub-acute concussion.

Specific Aims:

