Subjects will be both men and women, ages 18-60 years old, with a concussion resulting from a direct or indirect blow, rotation, or whiplash injury to the head or body. For the purposes of this study, we will define diagnosis of concussion/mTBI as those who have met the criteria set forth in this classification schema [23]:

Severity of Traumatic Brain Injury			
	GCS	PTA	LOC
Mild	13-15	<1 day	0-30 mins
Moderate	9-12	>1 to < 7 days	>30 mins to < 24 hrs
Severe	< 9	> 7 days	> 24 hrs

*GCS=Glasgow Coma Scale; PTA=Post-Traumatic Amnesia; LOC=Loss of Consciousness

However, as noted by the American Congress of Rehabilitation Medicine's statement on the definition of mTBI, "Due to the lack of medical emergency, or the realities of certain medical systems, some patients may not have the above factors medically documented in the acute stage. In such cases, it is appropriate to consider symptomatology that, when linked to a traumatic head injury, can suggest the existence of a mild traumatic brain injury [24]. When available, the study team will use medical records to confirm a patient's injury as an mTBI according to the schema above, however, if no records exist or are obtainable, clinical history and symptomatology will be used to confirm the diagnosis.

In Part A, subjects must be consented \leq 28 days post injury. In Part B, subjects must be consented, randomized, and start treatment within 24 hours of presentation to the Trauma Unit.

Subjects in both Part A and B will have a symptom severity score of ≥ 20 at the time of randomization in order to reduce the expected degree (number and severity) of spontaneous symptom resolution prior to study completion.

Subjects with pre-existing neurologic conditions other than mTBI (including cognitive dysfunction) will be excluded.

Subjects with concurrent long bone fractures or orbital fractures will be excluded.

Subjects receiving, or planning to receive, a continuous ketamine infusion while enrolled in study will be excluded.

Subjects with these known endocrinological abnormalities at baseline will be excluded from study: diabetes mellitus, excess or deficiency of growth hormone, cortisol, or prolactin. Exclusion from study for any other endocrinological abnormalities or diagnoses existing at baseline are ultimately up to the discretion of the study physician.

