In Part B the design will be randomized, double-blinded, and placebo-controlled with Arm 1 receiving OXE-103 and Arm 2 receiving placebo. The enrollment target will be 20 subjects receiving OXE-103 and 20 subjects receiving placebo. Up to 50 subjects may be enrolled in Arms 1 and 2 combined to allow for replacement of subjects who may not complete the study requirements.

In Part A Arm 1 and Part B both Arms 1 & 2, the maximum enrollment will be 80 subjects. For the Part A Arm 2 (non-treatment concurrent control) the minimum target enrollment will be 20 subjects, but there will be no maximum number.

We will randomize using the REDCap database. The database will be set up to share randomization allocation only with the statistician and Investigational Pharmacy. All subjects will be consented and either begin treatment within 24 hours of presentation to the Trauma Unit (for Part B) or ≤ 28 days post-injury (for Part A). For Part A, starting on Day 1, the treatment cohort (Arm 1) will receive OXE-103 40ug/kg twice daily by self-injection and the non-treatment control group (Arm 2) will begin their monitoring. For Part B, on Day 1 (within 24 hours of being admitted into the Trauma Unit) the treatment Arm will receive OXE-103 40ug/kg SC twice daily by self-injection and the placebo Arm will receive a placebo injection SC twice daily. OXE-103 and placebo will be maintained and dispensed by Investigational Pharmacy. Subjects will receive an 8-day supply of syringes pre-loaded with OXE-103 or placebo. Each cohort receiving OXE-103 or placebo will receive the 2nd set of syringes with OXE-103 or placebo at the Day 8 visit. Appropriate therapy that would be considered standard of care by the Principal Investigator or Co-Investigator will be administered or prescribed at any time during subjects' study participation.

Subject training

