6.5 Demographic and Baseline Characteristics

Age at randomization, sex, race, ethnicity and days since injury will be summarized with appropriate statistics for each treatment group. Days since injury will be calculated as randomization date – injury date. Age and days since injury will also be summarized categorically (Age: 18-25, 26-35, 36-45 and 46-55 years; Days since injury: ≤7, 8-14, 15-21, 22-28, >28 days).

Medical history/concurrent conditions will be summarized for each treatment group by International Classification of Diseases, Tenth Revision, Clinical Modification (ICD-10-CM) diagnoses obtained from BioPortal [1,2]. In this summary, a subject may be counted only once for each distinct diagnosis.

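### Part A is no longer randomised, but SAP 6.13 still plans no adjustment, so an imbalance in days since injury or entry PCSS would bias its between-arm difference by an amount and in a direction the documents do not fix

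*SAP*

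**What the plan says.** The protocol (March 2021, amendment 1.7) states under Proposed Clinical Trial: "In Part A we will compare an open-label treatment arm (OXE-103) to a non-treatment concurrent control arm". The Part A Day 1 flowsheet sets out how the arms form. Patients are first offered the drug. "If they decline, they will be offered participation in non-treatment control Arm". There is a second route into the control arm: "If subjects choose treatment and fail screening, they may be offered non-treatment control Arm option".

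Under Inclusion/Exclusion, Part A patients must consent within 28 days of injury and have a symptom severity score of at least 20. The threshold is there "in order to reduce the expected degree (number and severity) of spontaneous symptom resolution prior to study completion".

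The SAP (version 1.0, November 2020) predates this design. Its section 2 still describes Part A as 1:1 randomised, double-blind and placebo-controlled, and its section 1 says that its analyses override those in the protocol where the two differ. Section 6.13 reads "No statistical modeling is planned for this exploratory study, therefore, there will be no adjustment for covariates", and section 6.12 plans no subgroups. Section 6.5 tabulates days since injury by group, with the definition "Days since injury will be calculated as randomization date – injury date". Sections 4 and 6.1 say the data will be used to detect between-group trends, to provide sample sizes and power calculations for later studies, and to choose endpoints.

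**The concern.** With randomised arms, leaving out covariates costs some precision but introduces no bias. With arms formed by acceptance, refusal and screen failure, nothing in the design balances them. Two variables that plausibly govern recovery over the next 14 days are time since injury and the entry score, and both may differ between people who accept twice-daily injections and people who do not. Both are already collected, yet the plan reports raw arm summaries only.

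At stake is the Part A half of the primary objective, the change in symptom burden from Day 1 to Day 15. The ROC search in SAP 6.8 is affected too: if carried over to Part A, it would choose the cut-off that best separates two arms that may differ for reasons other than the drug. A biased difference used to size a later trial carries the bias forward, and a larger Part A would not remove it. Part A is open-label, so an adjustment chosen after the data are in could be chosen with the results in view.

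**Working it through.** The plan states no effect size, SD, control rate or power for Part A, so there is no figure to reproduce. The documents give no recovery curve and no data on who accepts or declines. Everything below assumes **no drug effect** and is illustrative.

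**A. Simple curve.** Assume that the share of symptoms resolving naturally over 14 days falls linearly from 60% for entry on day 1 to 30% for entry on day 28:

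f(t) = 0.60 − 0.30 × (t − 1)/27

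- f(11) = 0.60 − 0.30 × 10/27 = 48.9%
- f(18) = 0.60 − 0.30 × 17/27 = 41.1%

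1. *Entry time alone* (mean day 11 v 18): 0.30 × 7/27 = 7.8 percentage points in percent improvement. At a baseline of 40 in both arms this is 0.078 × 40 = 3.1 PCSS points.
2. *Baseline alone* (50 v 40, same recovery fraction): the mean change differs by 10 × 0.30 = 3.0, 10 × 0.45 = 4.5 or 10 × 0.60 = 6.0 points. Percent improvement is identical, so the 20% responder rate does not move.
3. *Both, with the later-entering arm also the worse-scoring arm*: 50 × 0.411 = 20.6 v 40 × 0.489 = 19.6, a net difference of 1.0 point. On absolute change the two biases largely cancel. The 7.8-point gap in percent improvement remains, and it runs against the later-entering arm.
4. *Both, with the earlier-entering arm the worse-scoring arm*: 50 × 0.489 = 24.4 v 40 × 0.411 = 16.4, a difference of 8.0 points. Here they add.

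The same two imbalances therefore give anything from 1 to 8 points, depending only on how they are paired.

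**B. A different recovery model, by simulation.** PCSS decays exponentially, with a recovery time that varies between patients (lognormal, median 20 or 40 days, log-SD 0.5 or 1.0). The injury-day score is 60 (SD 20), the noise SD is 6, entry requires a score of at least 20, and follow-up is 14 days. The adjusted figure is from a linear regression of change on arm, days since injury and entry PCSS.

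| Entry days centred on | Unadjusted difference in change (PCSS points) | Difference in 20% responder rate (percentage points) | Adjusted difference in change (PCSS points) |
|---|---|---|---|
| 14 v 14 | about 0 | 0.1 to 0.3 | about 0 |
| 10 v 17 | 2.3 to 4.4 | 2.6 to 6.2 | about 0 |
| 7 v 21 | 4.3 to 8.4 | 5.0 to 11.6 | within 0.5 of 0 |

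All the unadjusted differences favour the earlier-entering arm.

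**C. Scale against sampling error.** With 20 completers per arm, the 95% half-width for a difference in responder rates is 1.96 × √(2p(1 − p)/20). This is 31 percentage points at p = 0.5 and 25 at p = 0.8. The illustrated responder biases are smaller than this, but they are systematic.

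**D. Can the SAP's definitions carry an adjusted Part A analysis?** SAP 6.1 defines baseline as the last value before first dose, and Arm 2 has no dose. SAP 6.2 uses the per-protocol set, which requires at least 10 doses, for all efficacy summaries; Arm 2 would be empty. Its ITT set is all randomised subjects, and Part A has none. An adjusted model added to 6.13 alone would have no control arm.

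**The case against.** The strongest reply is that this is a descriptive pilot with no planned between-arm test. Days since injury is tabulated by group (SAP 6.5) and PCSS values are summarised by group and visit (SAP 6.8), so an imbalance would be seen. All of that stands, and it limits the harm: the risk is a misleading trend or planning figure, not a false claim of significance. But seeing an imbalance does not tell the reader how much of the difference it explains.

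A reader might also infer four stronger things that the documents do not support.

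- *That the bias will look like a benefit of OXE-103.* Nothing says who accepts and who declines. If acceptors are both worse and later after injury, the biases nearly cancel on absolute change and run against the drug on percent improvement. Under a single common exponential recovery rate, percent improvement would not depend on entry day at all.
- *That days since injury cannot be computed for Part A.* The formula names a randomisation date that Part A patients lack, but SAP 6.1 treats randomisation as Day 1 and both arms have a Day 1. This is stale wording, not a lost variable.
- *That the SAP forbids adjustment.* It plans none, but section 1 allows documented deviations.
- *That entry starts on the day of injury.* Only the upper limit of 28 days is stated, for patients described as sub-acute.

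It is also fair to say that section 6.13 is one symptom of a SAP not yet revised for amendment 1.7.

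**Conclusion.** The concern holds in a limited form. Part A is a non-randomised comparison, the condition is expected to improve partly on its own, and the governing SAP plans no adjustment for two collected variables likely to affect recovery. An imbalance in either would bias the raw between-arm difference and the planning estimates drawn from it.

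Neither direction nor size can be read from the documents. Under the assumed linear curve, a 7-day entry difference alone gives about 7.8 percentage points in percent improvement. Adding a 10-point higher baseline in the later-entering arm leaves a net of about 1 PCSS point on absolute change, and a baseline difference alone leaves the 20% responder rate unchanged. These figures rest wholly on the assumed recovery pattern and imbalances. The absence of adjustment is certain; the amount of bias is not. The change should be made, but the point does not show that Part A will mislead.

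**What to change.** In SAP 6.13, for Part A only, add beside the raw summaries the Arm 1 minus Arm 2 difference in change to Day 15 for PCSS severity, number of symptoms and 4MBS. Estimate each from a linear model with baseline score and days since injury as covariates, with a 95% CI. Prefer the adjusted figure to the raw one for any planning use. State residual confounding as a limitation: reasons for refusal, screen failure, open-label self-report and concomitant therapy.

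For this to run:

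- SAP 6.1: define baseline for Part A Arm 2 as the Day 1 value.
- SAP 6.2: define a Part A efficacy set that does not require doses in Arm 2.
- SAP 6.5: define days since injury for Part A as Day 1 date minus injury date (a wording correction).

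The cost is SAP wording and one extra table, with no new data. The downside is a simple two-covariate model in about 40 subjects within an otherwise descriptive plan. It reduces bias from the two measured variables only. The responder outcomes would remain as raw rates, to be read with the baseline table.
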